GAGES-C Assessment: for this assessment, subjects will perform a simulated colonoscopy on the Kyoto simulator. This will involve navigating to the cecum on a standardized case, followed by withdrawal and mucosal inspection to identify 5 numbered targets. For 3 of the targets, subjects will be asked to make contact with them using a standard biopsy forceps. External views of the endoscope and the subjects hands will be video recorded along with the endoscopic view combined into one screen using a video mixer. The recordings will then be scored using GAGES-C scoring system, which assesses scope navigation, use of strategies (loop reduction, positioning, etc), ability to keep a clear field, instrumentation (facility using tools) and quality of exam each on a anchored 5pt likert scale⁶. Evaluators using the scoring system will be blinded to the subjects group and training status.

Simulated Colonoscopy Objective Performance Evaluation (S.C.O.P.E): This is based on the framework of the Kyoto platform described above but has been modified into 4 separate tasks

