that include performance metrics and a scoring system. The tasks include *Scope Manipulation*: requires use of torque and tip deflection to move a shape in the colon to the 6 o'clock position and align that shape within an outline of the shape placed upon the monitor screen. Alignment must be held for 5 seconds for each shape before continuing to the next shape. The modified colon contains 10 shapes in various locations. *Tool Targeting*: requires coordination with biopsy forceps to contact a metal target, completing a circuit and sounding a tone. Contact must be maintained for 5 seconds on each target before continuing to the next. The modified colon segment contains 10 targets in various locations. *Loop Management*: perform scope navigation to correctly manage the formation of a standard alpha loop. The task is to insert the scope in the simulated rectum followed by navigation to the cecum through a redundant sigmoid. If a loop is formed, it must first be recognized and then successfully reduced to continue advancing the colonoscope. The task will begin in the left lateral decubitus position but on request, the task can be repositioned in the supine, prone, or right lateral decubitus position. Additionally, abdominal pressure can be provided by the proctor where and when directed by the subject. *Mucosal Inspection*: during withdraw of the colonoscope, identification of polyps placed randomly throughout a length of simulated colon and rectum requiring careful mucosal inspection, including retroflexion.

As an assessment, the tasks are administered sequentially by a proctor using a standard instruction script and standardized scoring metrics. As a training tool, subjects will train on each task until a defined expert performance proficiency level is reached.

Fundamentals of Endoscopic Surgery (FES): The manual skills portion of the FES program is based in virtual reality and delivered by either the GI Mentor II or Bronch Mentor simulators (Simbionix USA, Cleveland OH). It consists of 5 task that assess scope navigation, tool manipulation, loop reduction, retroflexion, and mucosal inspection. The exam is completely computer based and is administered by a proctor. All task instructions and scoring are completed by the computer based simulator and uploaded to a network server. The FES exam can only be given at FES test centers.

Methods:

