Phase I: *Establishing performance goals and references*- This phase will involve the ES group to define the task specific training goals for the novice curriculum. Each ES subject will complete a GAGES-C assessment followed by 3 trials of each of the S.C.O.P.E tasks. Three trials are used to help ensure that the simulator specific learning curve has been accounted for. The GAGES-C scores will be used to help calibrate performance of experienced endoscopist on the Kyoto model as the GAGES-C data to date has come from actual colonoscopies. The mean trial 3 performance on each of the S.C.O.P.E. tasks will be used to set the proficiency levels for the training curriculum to be utilized in Phase II.

Phase II: *Assessing the effects of the curriculum*- The NS group will be randomized in a 2:1 ratio between the training group (NST) and the control group (NSC) respectively. Both groups will undergo a pretest consisting of a GAGES-C assessment, a S.C.O.P.E assessment, and an FES assessment. Subjects in the NST group will then train to the proficiency levels established in Phase I for each of the S.C.O.P.E. tasks. The NST group will then undergo a posttest

[figure not shown]
consisting of a GAGES-C assessment, S.C.O.P.E assessment, and FES assessment within 2 weeks of completion of the curriculum. NSC subjects will receive no training during this phase and will return for the posttest after the same amount of time as it took for the NST group to complete their training. Both groups will be queried as to any additional clinical endoscopic experience that they received between the pretest and the posttest. Once the NSC subjects complete the posttest, they will be allowed to complete the curriculum if they wish, including an additional post curriculum assessment within 2 weeks of curriculum completion.

Phase III: Long term follow up- All subjects who complete the curriculum in both the NST and NSC groups will be asked to return for additional assessment at 6 months and 12 months. Subjects will be queried as to any additional clinical endoscopic experience that they received between the assessments. This follow up assessment will consist of 3 trials of each S.C.O.P.E. task to evaluate for rapid spontaneous recovery of skills seen in previous similar studies.³ They will also undergo an FES assessment.

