Data Analysis: For continuous variables, mean performance differences between pretest and posttest assessment within groups will be statistically assessed for significance using paired t-test. Mean performance differences between groups will be statistically assessed for significance with unpaired t-tests. Differences for multiple repeated measures during long term follow up will be assessed with repeated measure ANOVA. For proportions, rates of achieving a passing score on the FES assessment will be statistically assessed for significance using Fishers exact test or chi squared as appropriate.

Sample Size / Power Analysis

Samples size can be estimated using previous data for two of our primary endpoints stated in the hypothesis, GAGES-C and S.C.O.P.E. Previously published GAGES-C scores for novice and intermediate endoscopists⁶ showed a difference in means between the two groups of approximately 6, with a standard deviation in the novice group of 3.8 and intermediate group of 1.6. If we use a paired, two tailed t-test (since our subjects undergo a pre-test then a post-test) with alpha set at 0.05, estimated standard deviation of 5.5 and a power of 80%, then we need 9 subject to be able to reject the null hypothesis. Since the exact difference in performance improvement is unknown, Figure 1 shows sample size and power for a difference in means ranging from 3 to 6.

Similar calculations can be done using the S.C.O.P.E. score endpoint. Unpublished data currently undergoing peer review showed that for S.C.O.P.E score, novice and intermediate

endoscopists showed a difference in means between the two groups of approximately 115 with a standard deviation in the novice group of 94 and intermediate group of 62.⁹ If we apply the same paired, two tailed t-test with alpha set at 0.05, estimated standard deviation of 150 and a power of 80%, then we need 15 subject to be able to reject the null hypothesis. Since the exact difference in performance improvement is unknown, the graph below shows sample size and power for a difference in means ranging from 95 to 125.

[figure not shown]

Figure 2: Required sample size as a function of statistical power for differences in means between groups ranging from 95 - 125

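### Phase II randomises novices before the pretest without withholding the arm, so the baseline can be taken with the arm known and pretest losses count as post-randomisation losses

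*Protocol*

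**What the plan says.** The order of events is in the protocol under Methods, Phase II. It starts with "The NS group will be randomized in a 2:1 ratio between the training group (NST) and the control group (NSC) respectively". The next step is "Both groups will undergo a pretest consisting of a GAGES-C assessment, a S.C.O.P.E assessment, and an FES assessment". Training follows: "Subjects in the NST group will then train to the proficiency levels established in Phase I for each of the S.C.O.P.E. tasks". No allocation step stands between the pretest and training.

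The protocol describes how each assessment is run under Apparatus and Procedures:

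- **GAGES-C** is scored from video. "Evaluators using the scoring system will be blinded to the subjects group and training status".
- **FES** is run by the simulator. "All task instructions and scoring are completed by the computer based simulator and uploaded to a network server".
- **S.C.O.P.E.** is run in person: "the tasks are administered sequentially by a proctor using a standard instruction script and standardized scoring metrics". No blinding of the proctor is stated.

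Under Data Analysis, the pretest is one half of the within-group test: "mean performance differences between pretest and posttest assessment within groups will be statistically assessed for significance using paired t-test". For the comparison of arms the text is: "Mean performance differences between groups will be statistically assessed for significance with unpaired t-tests". It does not say whether posttest scores or changes from pretest are compared, and it describes no baseline adjustment.

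Under Sample Size / Power Analysis, a single 20% drop-out allowance is applied to each arm. It is not divided between losses before and after the pretest.

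**The concern.** A baseline is most useful when it is measured before anyone can react to the allocation. Here the arms exist when the pretest is taken, and nothing in the document keeps them hidden.

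Two things follow. First, a volunteer who knows the arm may try harder or less hard on any of the three tests, and a proctor who knows it is present throughout S.C.O.P.E. Second, a volunteer who leaves between allocation and pretest has already been randomised. That person cannot enter a paired analysis and leaves no scores to show whether the losses were selective.

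Subjects must learn their arm once training starts. The pretest is the one assessment at which ignorance of the arm can be secured completely, and at no cost.

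**Working it through.** **Step 1. The sequence.** Phase II gives: randomise 2:1, then pretest for both groups, then training for NST. The reference to both groups at the pretest confirms that the groups already exist. I found no statement elsewhere that allocation is concealed or withheld until the pretest is complete. The only masking statement concerns the GAGES-C video raters. The document does not say that the arm is disclosed at randomisation either, so the supportable wording is that the arm can be known at the pretest.

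**Step 2. Where knowledge of the arm could act.**

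| Test | Scoring | Subject effort |
|---|---|---|
| GAGES-C | protected (blinded raters) | exposed |
| FES | protected (computer) | exposed |
| S.C.O.P.E. | proctor, no blinding stated; limited by script and standard metrics | exposed |

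**Step 3. Which analyses would move.** Let knowledge of the arm shift the mean pretest by a in NST and by b in NSC, with posttests unchanged.

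- Paired mean change in NST moves by −a; in NSC by −b.
- Difference in mean change, NST minus NSC, moves by (−a) − (−b) = b − a.
- Difference in mean posttest moves by 0.
- Posttest FES pass rate moves by 0.

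The sign is open. If only the control pretest falls (a = 0, b < 0), the control gain is inflated and the change-score contrast shrinks. That works against the trial's superiority hypothesis. The document gives no value for a or b.

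**Step 4. The plan's own numbers.** The inputs are 24 training and 12 control subjects with 20% drop-out.

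- NST: 24 / (1 − 0.20) = 30.
- NSC: 12 / (1 − 0.20) = 15.
- Total: 30 + 15 = 45, as stated.

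The allowance is thus 30 − 24 = 6 in NST and 15 − 12 = 3 in NSC, for all causes over the whole study. If losses before the pretest fall within it, no planned figure changes.

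**Step 5. If such losses came on top of the 20%.** The rates below are assumptions that show sensitivity only. Completers are 24(1 − x) and 12(1 − x). The last column is the standardised between-arm difference detectable with 80% power by a two-sided unpaired t-test at 0.05.

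| Extra loss x | NST / NSC completers | Detectable difference (SD units) |
|---|---|---|
| 0 | 24 / 12 | 1.02 |
| 5% | 22.8 / 11.4 | 1.05 |
| 10% | 21.6 / 10.8 | 1.08 |
| 20% | 19.2 / 9.6 | 1.15 |

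Equal loss in both arms costs some power. Unequal loss is a question of bias, which no drop-out allowance repairs.

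**The case against.** The strongest reply is that early disclosure is inferred. The order rests on two summary sentences, and a figure in the Phase II text was not visible to me and might show another order. Drawing an allocation before baseline does not invalidate a randomised comparison; only disclosure would matter. This stands as a limit on the wording. It does not remove the point, because the text as written permits disclosure and nothing prevents it.

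Second, the scoring is largely protected. GAGES-C raters are blinded, FES is scored by machine, and the S.C.O.P.E. metrics named in the appended abstracts (completion times, missed polyps, loop reduction, retroflexion) leave little room for judgement. This also stands. What remains is mainly effort, and the conduct of one proctor-run test.

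Third, a volunteer who leaves on learning of control status might do so after the pretest too, and would still be a post-randomisation loss without a posttest. That is correct. Reordering removes only the losses that occur before the pretest; for later losses it ensures that baseline scores exist to describe who left.

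Some stronger readings are tempting but unsupported:

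- A reader might infer that the whole treatment comparison is biased. Step 3 shows that a shifted pretest does not touch a posttest-only comparison or the posttest FES pass rate, and the protocol does not fix which scores are compared between arms.
- A reader might infer greater loss among controls. Nothing in the document shows this: controls carry no training burden before the posttest and are offered the curriculum afterwards.
- A reader might treat the 20% allowance as the expected loss before the pretest. It is a whole-study figure.
- A reader might size a baseline-adjusted bias with the test-retest reliability of 0.6 in the appended abstract. That figure is for experts and is not a novice pretest-to-posttest slope, and the protocol describes no adjusted analysis.

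**Conclusion.** The point holds as a free improvement to the design. As written, novices are randomised before the pretest and the arm is not withheld, so subjects and the S.C.O.P.E. proctor can know it at baseline, and anyone lost before the pretest is randomised without a baseline. The analyses at risk from a shifted baseline are the within-group paired tests and, if used, a comparison of change scores. The size and direction of any shift, and the number and balance of any losses, cannot be derived from the document. The recruitment of 45 reproduces and is not called into question. The conclusion assumes that the sentence order in Phase II is the order intended and that no missing figure contradicts it.

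**What to change.** Reorder the opening of Phase II, for example:

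> All NS subjects complete the GAGES-C, S.C.O.P.E. and FES pretest. Only after a subject's pretest is complete is that subject's 2:1 allocation to NST or NSC made, or revealed, from a concealed list.

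If the sites already intend to withhold the arm until then, one sentence saying that subjects and proctors do not learn it before the pretest is complete is enough. People who leave before the pretest are then either never randomised (allocation made afterwards) or leave without knowing their arm (allocation revealed afterwards).

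The cost is the rewording of two sentences. No visits, staff or subjects are added, and the sample size calculation is unchanged.

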there are no computerized components of the model. In addition, the acquisition costs are affordable, with an initial investment of less than \$10,000 required to begin training.

Our preliminary data using the physical colonoscopy model and our SCOPE program have been encouraging. We have shown that SCOPE, based on the above four tasks, can be administered in less than 50 minutes per learner. We have identified the key metrics for incorporation into a scoring system and have accumulated validity evidence that the SCOPE scoring system objectively assesses the technical skills required to perform standard flexible endoscopy. For each of the four tasks, we have validity evidence that task scores reliably differentiate between novices, intermediates, and experts. Our data indicate that SCOPE is a reliable, simple program for simulating basic flexible endoscopy. SCOPE could be an ideal training platform to prepare for basic clinical endoscopy and FES testing.⁷⁻⁹

The goal of this proposal is to develop a proficiency based skills curriculum for FES using SCOPE. We will draw on the success of proficiency based training for FLS and apply the same methodologies to FES. A proficiency based skills curriculum for FES using SCOPE could help prepare learners for the FES examination and could foster the success of the entire FES program.

Hypothesis

Our hypothesis is that training to expert derived performance goals on a non-computer based flexible endoscopy simulator will allow a group of novice endoscopists to acquire a level of skill adequate to achieve a greater than 80% pass rate on the manual skills portion of the Fundamentals of Endoscopic Surgery (FES) assessment. After completing this proficiency based curriculum, these novice endoscopists will also demonstrate performance scores on the Global Assessment of Gastrointestinal Endoscopic Skills for Colonoscopy (GAGES- C) and Simulated Colonoscopy Objective Performance Evaluation (S.C.O.P.E.) assessments equivalent to intermediately experienced endoscopists (50 - 140 endoscopies). Finally, the group of novice endoscopists who complete this proficiency based curriculum will demonstrate significantly higher scores on FES, GAGES-C, and S.C.O.P.E when compared to a control group that simply undergoes repeat assessment without any formalized curriculum (to control for learning effect of repeated assessment).

Methods

Subjects: Two distinct categories of subjects will be needed:

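### The control posttest is matched to training time rather than to pretest-to-posttest time, so on the literal text the arms' mean retest intervals can differ by 0 to 14 days (a minor point)

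*Protocol*

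**What the plan says.** All of this is in the Protocol.

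- **Allocation (Methods, Phase II).** "The NS group will be randomized in a 2:1 ratio between the training group (NST) and the control group (NSC) respectively". No pairing of controls with trainees and no delayed start for controls is stated.
- **Trained arm (Phase II).** The posttest takes place "within 2 weeks of completion of the curriculum".
- **Control arm (Phase II).** Controls "will return for the posttest after the same amount of time as it took for the NST group to complete their training". No window is attached to this date.
- **Length of training (description of the S.C.O.P.E. tasks).** When S.C.O.P.E. is used for training, "subjects will train on each task until a defined expert performance proficiency level is reached". The Protocol fixes no duration.
- **Purpose of the control arm (Hypothesis).** The trained group is compared with "a control group that simply undergoes repeat assessment without any formalized curriculum (to control for learning effect of repeated assessment").
- **Outside experience (Phase II).** "Both groups will be queried as to any additional clinical endoscopic experience that they received between the pretest and the posttest".

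**The concern.** The rule for controls is plainly meant to equalise the time between the two tests, but it equalises a different quantity. It copies the training time and leaves out the wait between finishing training and being tested. It also refers to one time for the whole trained group, although each trainee finishes when he or she reaches proficiency. The text does not say whether that time is a mean, a median, a maximum or the time of a particular trainee. Nor does it say how trainees who never finish are counted, although the Sample Size section allows 20% drop-out (0.20 × 30 = 6 trainees).

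What is at stake is the one job given to this control arm. How much of a first test's practice effect survives to the second, and how much clinical endoscopy a resident picks up in between, can both depend on the interval. The interval is set after randomisation, so randomisation does not balance it. A visit-timing rule also belongs in the Protocol, because an analysis plan cannot alter posttest dates that have already passed.

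**Working it through.** The Protocol states no retest interval, so there is no figure to reproduce. The sample sizes do not depend on this point.

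**Inputs.** T_i is trainee i's training time (self-paced, value not given). d_i is the wait from completion to posttest (0 to 14 days, Phase II). T_group is the trained group's training time (statistic not defined, Phase II).

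**Step 1: the two intervals.**
- Trained subject: T_i + d_i
- Control: T_group

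**Step 2: the difference in arm means.** If T_group is the mean of the T_i, then mean(T_i + d_i) − T_group = mean(d_i). Since every d_i lies between 0 and 14 days, so does the difference in means.

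**Step 3: relative size.** Training durations are assumed, because the Protocol gives none. The maximum relative excess is 14 / (7 × weeks). The last column assumes waits spread evenly over the window, a mean of 7 days, giving 7 / (7 × weeks).

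| Assumed training (weeks) | Excess if every trainee waits 14 days | Excess if the mean wait is 7 days |
|---|---|---|
| 2 | 100% | 50% |
| 4 | 50% | 25% |
| 8 | 25% | 12.5% |
| 12 | 17% | 8.3% |

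If trainees are tested on the day they finish, the excess is 0 in every row.

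**Step 4: individual mismatch.** Suppose, for illustration only, that training times run from 2 to 6 weeks with a mean of 4. Against a control interval of 4 weeks, a fast trainee tested at once differs by 2 + 0 − 4 = −2 weeks. A slow trainee tested at the end of the window differs by 6 + 2 − 4 = +4 weeks. Equal means would still leave unequal spreads.

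**Step 5: dependence on the undefined statistic.** With the same illustrative times, if T_group were read as the longest training time, the difference in means would be 4 + (0 to 2) − 6, that is −2 to 0 weeks. The sign can therefore change with the reading a site chooses.

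**Step 6: direction of any bias when the trained interval is longer.**
- Trained skill has longer to decay: works against training.
- Controls keep more of the practice effect of their pretest: works against training.
- Trainees have longer to gain outside endoscopy: works for training.

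The Protocol gives no figure for any of these, so neither the net direction nor the size in score points can be derived.

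**The case against.** The strongest reply is that this is a wording gap and little more. The two weeks are a ceiling that includes day 0, so there need be no gap if trainees are tested promptly. The intent of the control rule is clear, and a site may apply it sensibly. Outside endoscopy, the one route that would favour training, is asked about in both arms. The subjects have done fewer than 10 endoscopies, and the Background says the FES tasks are not open for practice. The remaining routes are conservative. Training to an expert-derived standard is being compared with no training, and a difference of days is unlikely to change that conclusion.

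Most of this stands, and it is why the point is minor. It does not remove the point. The query records outside exposure without equalising it, and it says nothing about decay or retained practice. The literal text still times the arms by different rules.

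Two stronger readings are tempting, and the documents do not support them.

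- **That the trial is biased in favour of the curriculum.** Step 6 shows effects in both directions. The percentages in Step 3 are shares of an interval under assumed durations, not effects on scores.
- **That early controls cannot follow the rule because the group time is not yet known.** A simulation had 98% to 100% of controls falling due before the last trainee finished. It assumed 30 trainees and 15 controls enrolled together over 0, 4, 12 or 26 weeks, mean training of 4 or 8 weeks with a log-SD of 0.4, and the group time read as a final mean. The Protocol states no enrolment pattern. A site could start a cohort together and retest its controls when its trainees finish, or match a control to an earlier finisher. The text neither requires nor forbids either.

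**Conclusion.** The point holds as a minor one. On the literal text of Phase II, with the group time read as a mean, the trained arm's pretest-to-posttest interval is on average 0 to 14 days longer than the control arm's. A single group time also cannot match self-paced individual times. The 14-day limit comes from the Protocol; every percentage rests on an assumed training duration.

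The direction of any bias is unclear. Its size is probably small beside the planning differences of about 6 GAGES-C points and about 115 S.C.O.P.E. points, but that is a judgement and not a computed result. No stated sample size, alpha or test is affected. The rule should be reworded because the change is cheap and protects the stated purpose of the control arm.

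**What to change.** Reword the control rule in Phase II as follows.

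- Define the control interval as time from pretest to posttest, not as training time, and give both arms the same posttest window.
- After randomisation, and before training times are known, yoke each control to one pre-selected trainee at the same site. The trainee should be one pretested no later than the control; otherwise the due date may already have passed.
- When that trainee is posttested, call the control for posttest at the same elapsed time since the control's own pretest, within a short window stated in days.
- If the trainee drops out, re-yoke the control to the next finisher at the site and record the change. These matches will be less close.

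With 10 trainees and 5 controls planned per site, there are enough trainees to yoke to.

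Two apparently natural alternatives should be avoided. Fixed randomisation blocks of three make the last assignment predictable once the first two are known, and the arms here cannot be masked from subjects or staff. Scheduling a control at the mean interval of two trainees fails because, if all three are pretested together, the mean is known only when the slower trainee is tested. By then the mean date has passed unless both took equally long.

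The change adds no subjects and no assessments. Its cost is less predictable scheduling for controls, and a log at each site linking each control to a trainee.

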Methods: Four tasks were created to evaluate the core skills for diagnostic endoscopy using the Kyoto Kagaku colonoscopy model (Kyoto Kagaku Co Ltd, Japan) as a base platform. The four tasks include: **Scope Manipulation** requiring use of torque and tip deflection to align a shape in the colon with a matching shape on the monitor screen. **Tool Targeting** requires coordination with biopsy forceps to contact a metal target. **Loop Management** requires prevention, recognition and reduction of a redundant sigmoid colon with navigation to the cecum. **Mucosal Inspection** requires identification of simulated polyps placed randomly throughout a length of simulated colon and rectum, including retroflexion. Key performance metrics were identified and a scoring system developed based on these parameters. Scores for each task were normalized to allow equal weighting for all four tasks. Thirty-five subjects were recruited for this prospective study and stratified into 3 cohorts based on colonoscopy experience: novice (0-50 colonoscopies)(n=11), intermediate(51-139)(n=13), and experts (>140)(n=11). Subjects performed 2 trials of all 4 of the above tasks. Mean normalized scores were compared between groups for both the individual tasks and the total S.C.O.P.E. score by one way ANOVA. Test-retest reliability was determined using intraclass correlation coefficient.

Results: Across all four tasks, experts (E) consistently outperformed intermediates (I), who, in turn, outperformed novices (N). These differences were statistically significant for all tasks. Mean normalized scores with 95% confidence intervals for each group on each task are as follows: **Scope Manipulation** [N-54 (26-82), I-90 (77-104), E- 106 (93-118) , p=0.0007], **Tool Targeting** [N-40 (24-55), I-79 (65-93), E-88 (72-105) , p < 0.0001], **Loop Management** [N-51 (24-79), I-78 (57-99), E- 101(98-105), p=0.003], **Mucosal Inspection** [N-73 (53-92), I-87 (77-96), E-100 (91-108), p= 0.013], and **Total S.C.O.P.E. Score** [N- 218(155-280), I-334 (296-372), E-395 (371-419), p<0.0001]. Initial Test - retest reliability for the expert Total S.C.O.P.E. score was respectable at 0.6.

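### The randomised comparison should adjust for the pretest and allow unequal variances; the power gain depends on a correlation the protocol does not give

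*Protocol*

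**What the plan says.** The Hypothesis section states that trained novices "will demonstrate significantly higher scores on FES, GAGES-C, and S.C.O.P.E when compared to a control group", and explains that the control group is there to account for learning from repeated testing. Methods, Phase II sets the design: "The NS group will be randomized in a 2:1 ratio between the training group (NST) and the control group (NSC) respectively", and "Both groups will undergo a pretest consisting of a GAGES-C assessment, a S.C.O.P.E assessment, and an FES assessment".

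Data Analysis names two tests for continuous scores before follow-up. Within arms, "mean performance differences between pretest and posttest assessment within groups will be statistically assessed for significance using paired t-test". Between arms, "Mean performance differences between groups will be statistically assessed for significance with unpaired t-tests". The second sentence does not say whether the t-test is pooled or Welch, or whether it is applied to posttest scores or to changes from pretest. No covariate is mentioned.

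Sample Size / Power Analysis gives, for GAGES-C, a "standard deviation in the novice group of 3.8 and intermediate group of 1.6"; for S.C.O.P.E. the corresponding SDs are 94 and 62. It plans on 24 evaluable trained subjects and about 12 controls. The only reliability figure is in an appended abstract: "Initial Test - retest reliability for the expert Total S.C.O.P.E. score was respectable at 0.6".

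**The concern.** The pretest is the baseline measurement most likely to predict the posttest, and the trial already collects it on every novice. The only analysis that explicitly uses it is the within-arm paired test, which cannot separate training from the effect of taking the test twice. The comparison that can separate them has only about 36 evaluable subjects and names no adjustment.

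There is a second, independent issue. The hypothesis is that trained novices reach intermediate level, and the protocol's intermediates are less variable than its novices. Under 2:1 allocation the smaller arm would then have the larger SD, which is the pattern in which a pooled t-test understates its standard error.

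At stake are precision on the main randomised contrast and the honesty of its intervals.

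**Working it through.** **Inputs.** From Sample Size / Power Analysis: two-sided alpha 0.05; 24 and 12 evaluable; SDs 3.8 and 1.6 (GAGES-C), 94 and 62 (S.C.O.P.E.); differences 3 to 6 and 95 to 125. Assumed: normal scores; pretest and control posttest at the novice SD; trained posttest at the intermediate SD; pre-post correlation r from 0 to 0.7.

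**The plan's own figures.**
- Paired t, GAGES-C, 6/5.5: n = 9 (power 81.7%), as stated.
- Paired t, S.C.O.P.E., 115/150: n = 16 (n = 15 gives 78.8%), against 15 stated.
- Controls: the calculation is not shown. A two-sample t at 2:1 with 6/5.5 needs 11, close to the stated 12. With 115/150 it needs 21, so 12 is reproduced on the GAGES-C inputs only.
- Dropout: 24/0.8 = 30 and 12/0.8 = 15, as stated.

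**Can r be recovered from the documents?** The SD of a paired difference satisfies SD² = s1² + s2² − 2·r·s1·s2.
- GAGES-C: r = (14.44 + 2.56 − 30.25)/(2 × 3.8 × 1.6) = −1.09, which is impossible.
- S.C.O.P.E.: r = (8836 + 3844 − 22500)/(2 × 94 × 62) = −0.84.

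The planning SDs of 5.5 and 150 therefore give no usable value. The 0.6 in the abstract is test-retest in experts on S.C.O.P.E., not novice pretest to posttest across training. Hence the range.

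**Pooled standard error under the documented SDs.**
- GAGES-C: true variance of the difference 2.56/24 + 14.44/12 = 1.310. Pooled: [(23 × 2.56 + 11 × 14.44)/34] × (1/24 + 1/12) = 6.404 × 0.125 = 0.800. SE ratio √(0.800/1.310) = 0.78.
- S.C.O.P.E.: true 3844/24 + 8836/12 = 896.5. Pooled 5459 × 0.125 = 682.4. SE ratio √(682.4/896.5) = 0.87.

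**Type I error, equal means, 24 vs 12** (simulation: 200,000 runs for the t-tests on posttest, 20,000 per setting for the rest; ranges are over r):

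| Method | GAGES-C | S.C.O.P.E. |
|---|---|---|
| Pooled t, posttest | 12.8% | 8.7% |
| Welch t, posttest | 5.1% | 5.0% |
| Pooled t, change | 5.1–7.2% | 5.7–6.3% |
| ANCOVA, ordinary errors | 12.7–13.0% | 8.3–8.8% |
| ANCOVA, HC2 | 6.4–6.7% | 5.8–6.1% |
| ANCOVA, HC3 | 5.1–5.4% | 4.7–5.0% |

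With equal SDs the pooled t-test gives 5.0%. The ordinary-error ANCOVA row shows that pretest adjustment alone does not repair the error rate.

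**Power at the smallest planning differences** (20,000 runs per setting):

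| r | S.C.O.P.E. 95: ANCOVA-HC3 / Welch posttest / Welch change | GAGES-C 3: same order |
|---|---|---|
| 0 | 82.8 / 84.2 / 52.1% | 67.4 / 67.6 / 36.6% |
| 0.3 | 86.7 / 84.9 / 67.0% | 70.7 / 67.2 / 47.6% |
| 0.5 | 91.3 / 84.2 / 80.0% | 77.5 / 68.0 / 59.7% |
| 0.6 | 94.8 / 84.1 / 88.1% | 81.7 / 67.7 / 68.5% |
| 0.7 | 97.6 / 84.6 / 94.7% | 88.3 / 68.3 / 78.4% |

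Gain over Welch on posttest: −1.4 and −0.2 points at r = 0; 1.8 and 3.5 at 0.3; 7.1 and 9.5 at 0.5; 10.7 and 14.0 at 0.6. At differences of 115 and 6, Welch on posttest already has 94.8% and 99.8% power.

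**Worst case examined.** Equal SDs of 94, difference 95, r = 0: ANCOVA-HC3 74.9%, pooled t 79.9%, Welch 78.4%.

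**The case against.** **An unpaired t-test need not be pooled or posttest-only.** This stands as a limit. Welch is an unpaired t-test, and the wording could mean change scores, in which case the pretest is already used and the inflation is small. The choice might also be made in an analysis plan not shown here. But the named method still leaves out the adjustment: across the range of r, ANCOVA-HC3 had more power than a change-score t-test, even the pooled one (for GAGES-C 3, 77.5% against 65.1% at r = 0.5).

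**The inflated error rates describe an odd null.** They need equal means together with a trained arm whose spread has shrunk. If training does nothing, both arms keep the novice SD and the pooled test holds 5%. This stands. The practical consequence is intervals that are too narrow when training does reduce spread, not a general false-positive rate of 8.7% or 12.8%.

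**The pooled test looks more powerful.** At a GAGES-C difference of 3 it rejects about 84 to 85% of the time, more than ANCOVA-HC3 until r is about 0.7. That advantage comes from its inflated error rate, so Welch is the fair comparator.

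**The retest effect is already handled.** Largely true: the control arm and its own test exist for this, and nothing says the paired tests replace that comparison. What remains is that the plan does not say which result carries the conclusion.

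**Stronger readings to avoid.** A reader might infer that adjustment is a free gain, or take the textbook factor 1 − r² at r = 0.6 as a promised 36% cut in variance. That factor assumes equal variances and a correlation the documents do not supply, and training to a fixed proficiency level could weaken the link between pretest and posttest. A reader might also infer, because Phase II describes randomisation before the pretest, that subjects know their arm at baseline. The text does not say when allocation is disclosed.

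**Conclusion.** The point holds in a conditional form. The protocol fixes a between-group method that names no use of a pretest collected in both arms, and a better method is available at this sample size. The benefit is worth having if the novice pre-post correlation is around 0.5 or more, modest at 0.3, and absent at 0. It concerns the low end of the planning differences.

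The unequal-variance issue is separate. It arises only if the test is pooled, applied to posttest scores, and training narrows the spread as the intermediate SDs suggest; pooled standard errors would then be about 78% (GAGES-C) and 87% (S.C.O.P.E.) of their true size. No SD is given for FES scores, so neither effect can be sized for that measure. This is an improvement the plan should make, not an error that invalidates the trial.

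**What to change.** In Data Analysis, make the primary between-group analysis of each continuous score an ANCOVA of posttest on arm and pretest, with HC3 standard errors and t reference. HC2 runs slightly high at this size. Site may be added; in simulation that kept type I error at 4.3 to 4.8% and cost about 1 to 3 power points. Name Welch for any remaining unpaired t-test. State that the conclusion on the curriculum's effect rests on this comparison, and that within-arm paired tests are descriptive. If power is quoted, show it over a range of r. FES pass rates stay with the stated tests for proportions.

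The cost is a change of wording, one degree of freedom for the pretest and two more if the three sites enter, and about 5 power points against the pooled t-test if SDs are equal and the correlation is zero. No extra subjects or assessments are needed.
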